4.3.6 Rationale for Endpoints

Efficacy Endpoints

This primary objective of this pilot study is to determine the sensitivity and specificity of ferumoxytol steady state imaging in distinguishing true progression in subjects who will receive standard of care chemoradiation with Immunotherapy (pembrolizumab) for glioblastoma.

The secondary endpoints will provide preliminary data on safety, toxicity, and efficacy (progression free survival, overall survival, best response and duration of best response survival) in glioblastoma receiving pembrolizumab in addition to standard of care treatments. Data from this pilot study will be used to power a larger study.

Biomarker Research End Points

Blood Biomarker

The number and type of systemic and tumor infiltrating T cell may suggest response to immunotherapy in various cancers.[39] This exploratory study will look at serum immune cell subtypes at various time points and correlate them with radiographic and clinical outcomes. This is further elaborated in section 8.3.1.

Tissue Biomarker

The type and number of tumor infiltrating immune cells including lymphocytes and macrophages correlate with outcomes and prognosis in solid tumors [70]. There is emerging evidence that there is a correlation between the immunophenotype and PD-L1 expression to treatment response in a variety of solid tumors. [85-88] However, limited data is available regarding brain tumors. This study will explore the changes in the PDL-1 expression (before and after therapy with pembrolizumab) and types of tumor infiltrating immune cells with

radiographic and clinical outcomes in primary and metastatic brain tumors. This is further elaborated on in section 8.3.2.

5.0 METHODOLOGY

5.1 Diagnosis/Condition for Entry into the Trial

Due to the innate differences in the pathology, natural history and differences in current standard of care for primary and metastatic brain tumors this pilot study will have two arms:

ARM 1: Metastatic brain tumors: Melanoma (closed to enrollment)

ARM 2: Primary brain tumor: Glioblastoma multiforme (GBM)

5.2 Subject Inclusion Criteria

In order to be eligible for participation in this trial, the subject must:

1. Be willing and able to provide written informed consent/assent for the trial.
2. Be ≥ 18 years of age on day of signing informed consent.
3. Have a life expectancy of at least 6 months.
4. Have a histologically confirmed diagnosis of: newly diagnosed glioblastoma (WHO Grade IV)
5. Have ECOG performance status of 0 or 1 on stable or reducing dose of steroids for symptom management (not more than 8 mg of dexamethasone or equivalent per day) for 5 days prior to enrollment. Change in glucocorticoid dose for any purpose other than to modulate symptoms from an adverse event. *Note: The use of physiologic doses (e.g., prednisone 10 mg) of corticosteroids may be approved after consultation with Merck & Co. Use of prophylactic corticosteroids to avoid allergic reactions (e.g. IV contrast dye) is permitted.*
6. At least 14 days from any major surgeries including brain biopsy before the start of study drug pembrolizumab.
7. Demonstrate adequate organ function as defined in Table 3.
8. Female subject of childbearing potential should have a negative urine or serum pregnancy within 72 hours prior to receiving the first dose of study medication. If the urine test is positive or cannot be performed or confirmed as negative, a serum pregnancy test will be required.
9. Female subjects of childbearing potential should be willing to use 2 methods of birth control or be surgically sterile, or abstain from heterosexual activity for the course of the study through 120 days after the last dose of study medication. Subjects of childbearing potential are those who have not been surgically sterilized or have not been free from menses for > 1 year. Male subjects should agree to use an adequate method of contraception, including but not limited to, abstinence from heterosexual activity starting with the first dose of study therapy through 120 days after the last dose of study therapy.
10. Subject is eligible for and agrees to receive standard of care radiation and temozolamide after biopsy or maximum safe surgical resection.

Table 3 Adequate Organ Function Laboratory Values

System	Laboratory Value
--------	------------------

Hematological	
Absolute neutrophil count (ANC)	≥1,500 /mcL
Platelets	≥100,000 / mcL
Hemoglobin	≥9 g/dL or ≥5.6 mmol/L without transfusion or EPO dependency (within 7 days of assessment)
Renal	
Serum creatinine OR Measured or calculated ^a creatinine clearance (GFR can also be used in place of creatinine or CrCl)	≤1.5 X upper limit of normal (ULN) OR ≥60 mL/min for subject with creatinine levels > 1.5 X institutional ULN
Hepatic	
Serum total bilirubin	≤ 1.5 X ULN OR Direct bilirubin ≤ ULN for subjects with total bilirubin levels > 1.5 ULN
AST (SGOT) and ALT (SGPT)	≤ 2.5 X ULN OR ≤ 5 X ULN for subjects with liver metastases
Albumin	≥2.5 mg/dL
Coagulation	
International Normalized Ratio (INR) or Prothrombin Time (PT)	≤1.5 X ULN unless subject is receiving anticoagulant therapy as long as PT or PTT is within therapeutic range of intended use of anticoagulants
Activated Partial Thromboplastin Time (aPTT)	≤1.5 X ULN unless subject is receiving anticoagulant therapy as long as PT or PTT is within therapeutic range of intended use of anticoagulants
^a Creatinine clearance should be calculated per institutional standard.	

5.3 Subject Exclusion Criteria

The subject must be excluded from participating in the trial if the subject:

1. Has a diagnosis of immunodeficiency including Human Immunodeficiency Virus (HIV) (HIV 1/2 antibodies) and is not on continuous daily immunosuppressive therapy within 7 days prior to the first dose of trial treatment. (An exception to this is the use of steroids for brain edema and resulting symptoms. Subjects may receive a stable or reducing dose of steroids (up to 8 mg dexamethasone or equivalent for at least 5 days prior to signing consent) to prevent or manage cerebral edema. Subjects requiring over 8mg of dexamethasone per day on or five days prior to signing consent are excluded).
2. Has a known history of active TB (Bacillus Tuberculosis)
3. Hypersensitivity to pembrolizumab or ferumoxytol or any of their excipients.
4. Has had a prior anti-cancer monoclonal antibody (mAb) within 4 weeks prior to study Day 1 or who has not recovered (i.e., ≤ Grade 1 or at baseline) from adverse events due to agents administered more than 4 weeks earlier.
5. Has a known additional malignancy that is progressing or requires active treatment. Exceptions include basal cell carcinoma of the skin or squamous cell carcinoma of the skin that has undergone potentially curative therapy or in situ cervical cancer.
6. Has active autoimmune disease that has required systemic treatment in the past 2 years (i.e. with use of disease modifying agents, corticosteroids or immunosuppressive drugs). Replacement therapy (eg thyroxine, insulin, or physiologic corticosteroid replacement therapy for adrenal or pituitary insufficiency, etc.) is not considered a form of systemic treatment.
7. Has known history of, or any evidence of active, non-infectious pneumonitis.
8. Has an active infection requiring systemic therapy.

9. Has a history or current evidence of any condition, therapy, or laboratory abnormality that might confound the results of the trial, interfere with the subject's participation for the full duration of the trial, or is not in the best interest of the subject to participate, in the opinion of the treating investigator.
10. Has known psychiatric or substance abuse disorders that would interfere with cooperation with the requirements of the trial.
11. Is pregnant or breastfeeding, or expecting to conceive or father children within the projected duration of the trial, starting with the pre-screening or screening visit through 120 days after the last dose of trial treatment.
12. Has known active Hepatitis B (e.g., HBsAg reactive) or Hepatitis C (e.g., HCV RNA [qualitative] is detected).
13. Has received a live vaccine within 30 days of planned start of study therapy.
Note: Seasonal influenza vaccines for injection are generally inactivated flu vaccines and are allowed; however intranasal influenza vaccines (e.g., Flu-Mist®) are live attenuated vaccines, and are not allowed.
14. Subjects with clinically significant signs of uncal herniation, such as acute pupillary enlargement, rapidly developing motor changes (over hours), or rapidly decreasing level of consciousness, are not eligible.
15. Subjects with known allergic or hypersensitivity reactions to parenteral iron, parenteral dextran, parenteral iron-dextran, or parenteral iron-polysaccharide preparations (Ferumoxytol Investigator's Drug Brochure, 2009). *Subjects with significant drug or other allergies or autoimmune diseases may be enrolled at the investigator's discretion.*
16. Subjects who have a contraindication for 3T MRI: metal in their bodies (a cardiac pacemaker or other incompatible device), or are severely agitated.
17. Subjects with known iron overload (genetic hemochromatosis). In subjects with a family history of hemochromatosis, hemochromatosis must be ruled out prior to study entry with normal values of the following blood tests: Transferrin saturation (TS) test and Serum ferritin (SF) test. All associated costs will be paid by the study.
18. Subject who have received ferumoxytol within 3 weeks of study entry.
19. Subjects with three or more drug allergies from separate drug classes.

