4.3.4 Clinical Studies

4.3.4.1 Registrational program

From Ferumoxytol Investigator's Brochure 2009:

The ferumoxytol clinical development program was comprised of eleven studies. These included three Phase 1 studies (two dose-escalation studies and a study of the electrocardiographic/QTc effects of ferumoxytol), two Phase 2 studies that evaluated the safety and efficacy of ferumoxytol for iron replacement in patients with Chronic Kidney Disease (CKD), and two Phase 2 imaging studies that assessed the feasibility of ferumoxytol as an MRI contrast agent. There were three open-label, Phase 3 studies that examined the efficacy and safety of ferumoxytol relative to oral iron in patients with CKD, Stages 1-5, either on or not on dialysis. A fourth Phase 3 study in patients with any stage of CKD evaluated the safety of ferumoxytol relative to placebo in a cross-over, double-blinded manner. Ferumoxytol has been evaluated at exposures of up to 2 x 510 mg, including two courses of 2 x 510 mg in three of the four Phase 3 studies. Specifically, the following regimens of ferumoxytol were given during the clinical program:

- ≤ 4 mg Fe/kg
- 1x 125 mg
- 1x 250 mg
- 1x 510 mg
- 8x 128 mg
- 4x 255 mg
- 2x 510 mg

Approximately 1,740 patients were exposed to ferumoxytol in the entire AMAG clinical development program, including approximately 1,509 patients in the Phase 3 studies. Only one patient (0.06% of all patients exposed to ferumoxytol) experienced an anaphylactoid reaction following treatment with ferumoxytol; this patient had a history of multiple drug allergies and experienced an anaphylactoid reaction (hot flashes and itching, with no respiratory compromise) and severe hypotension a few minutes after receiving ferumoxytol.

There have been no deaths that were considered to be related to ferumoxytol treatment. There were 28 deaths in the clinical program, all of which have occurred in Phase 3 studies, with 16 deaths among the 1,740 patients exposed to ferumoxytol (0.9%) and 8 deaths among the 296 patients exposed to oral iron (2.7%). Four deaths occurred in patients who had signed an informed consent for enrollment but did not receive any iron agents. All deaths in the clinical

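### Exclusion criterion 1 is worded backwards: it bars only immunodeficient subjects who are off immunosuppression, and so contradicts its own steroid exemption

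*Combined protocol and SAP*

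**What the plan says.** The list in Section 5.3 opens "The subject must be excluded from participating in the trial if the subject", so meeting any one item excludes. Criterion 1 then names a subject with an immunodeficiency diagnosis, HIV included, "and is not on continuous daily immunosuppressive therapy within 7 days prior to the first dose of trial treatment". In parentheses it exempts steroids given for brain edema, at a stable or reducing dose of up to 8 mg dexamethasone or equivalent. It ends by excluding subjects who need more than 8 mg a day.

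Three other items in the list bear on the same subjects:

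- Criterion 6: "Has active autoimmune disease that has required systemic treatment in the past 2 years", with replacement therapy exempted.
- The note under criterion 15: "Subjects with significant drug or other allergies or autoimmune diseases may be enrolled at the investigator's discretion".
- Criterion 19: "Subjects with three or more drug allergies from separate drug classes".

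Inclusion 5 (Section 5.2) repeats the 8 mg cap. Its note allows physiologic corticosteroid doses after consultation with the drug supplier, and prophylactic steroids against allergic reactions.

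**The concern.** Criterion 1 is an operative eligibility rule, and its literal sense runs opposite to the sense that its own exemption needs. The investigator signs a completed eligibility review for each subject (Section 7.2). An investigator who follows the text lets continuous immunosuppression pass this criterion. One who follows the evident intent departs from the approved text.

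The protocol regards immunosuppression as undesirable with pembrolizumab. Section 4.0 says steroids can dampen the immune response, and Section 7.17.2 says, in its item on natural and herbal products, that immune suppressants may reduce efficacy.

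The wording also reaches beyond enrolment. Section 7.17 carries the medications prohibited in the exclusion criteria into the treatment period, and Section 5.4.2 ties retreatment to safety parameters in the inclusion and exclusion criteria.

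A lesser question is the note under criterion 15. It gives discretion over allergic and autoimmune subjects in general terms, while criteria 6 and 19 exclude some of those subjects outright.

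**Working it through.** No sample size, power or error rate is involved. The check is a truth table and a comparison of the criteria.

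**Step 1: criterion 1 as written.** Let A = diagnosis of immunodeficiency and B = continuous daily immunosuppressive therapy within the 7-day window. The lead-in makes the listed condition the ground for exclusion, so the text excludes A AND (NOT B). If B is itself a ground for exclusion alongside A, the rule is A OR B.

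| A | B | Text: A and not B | Implied: A or B |
|---|---|---|---|
| yes | no | excluded | excluded |
| yes | yes | not excluded | excluded |
| no | yes | not excluded | excluded |
| no | no | not excluded | not excluded |

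The text bars 1 of 4 combinations and the implied rule bars 3 of 4. They differ in 3 − 1 = 2 combinations, which are exactly the two with B present.

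**Step 2: which direction is intended.** The exemption for edema steroids follows directly. Exempting one kind of immunosuppressant is needed only if immunosuppression would otherwise exclude. The closing sentence, which excludes higher steroid doses, points the same way. The exemption is addressed to subjects generally, not only to those with immunodeficiency, so A OR B fits it best. Any reading in which B counts against the subject conflicts with the text as written.

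**Step 3: what the rest of the protocol still catches.** A subject who escapes criterion 1 is not thereby eligible.

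| Subject's therapy | Caught elsewhere? |
|---|---|
| More than 8 mg dexamethasone a day | Yes: last sentence of criterion 1, and inclusion 5 |
| Systemic treatment in the past 2 years for active autoimmune disease | Yes: criterion 6 |
| Chemotherapy or biological therapy outside the protocol | Section 7.17.2, during screening and treatment; may catch some agents |
| Other continuous non-steroid immunosuppression, with or without immunodeficiency (for example after an organ transplant) | Only by investigator opinion under criterion 9 |

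The last row is the practical gap.

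**Step 4: carry-over into the trial.** Section 7.17 takes on-trial prohibitions from the exclusion list. Read literally, criterion 1 prohibits no immunosuppressant apart from steroids above the stated cap, so the carry-over rule has little to attach to.

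**Step 5: the note under criterion 15.** Its reference to autoimmune disease is wide enough to include the criterion 6 group, and its reference to allergies can include the criterion 19 group. The note does not mention either criterion, and Section 5.3 states no order of precedence. Two readings are open: the note yields to criteria 6 and 19, or it qualifies them.

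**The case against.** The strongest reply is that exclusion criteria are disjunctive, so a defect in one does not admit anyone. Steroid doses above the cap, treated active autoimmune disease and any therapy the investigator thinks confounding all remain barred. The intent is plain from the exemption, the trial runs at a single institution, and the investigator signs every eligibility review, so misapplication is unlikely. Most of this stands, and it narrows the gap to the last row of Step 3. It does not repair the criterion: criterion 9 rests on opinion, and a mandatory rule should not depend on readers reversing it.

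A reader might infer that the note under criterion 15 lets the investigator enrol subjects whom criteria 6 and 19 bar. The text does not establish that. Because any single exclusion suffices, the note can sit beside those criteria and cover inactive or long-untreated autoimmune disease, one or two drug allergies, and non-drug allergies. It is an ambiguity, not a proven override.

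A reader might also connect the note to the one anaphylactoid reaction among about 1,740 patients exposed to ferumoxytol, of whom Section 4.3.4.1 says "this patient had a history of multiple drug allergies and experienced an anaphylactoid reaction". That account gives neither the number nor the classes of the allergies. Placing such a patient in the group the note admits assumes that the note defeats criterion 19, which is the point left open.

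**Conclusion.** Criterion 1 is wrong as written and should be corrected. In logical terms it misses both combinations in which the subject is immunosuppressed. In practice the gap is continuous non-steroid immunosuppression given for a reason other than active autoimmune disease, including in immunodeficient subjects, with only criterion 9 behind it. The note under criterion 15 needs a clarification and no more.

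It would be tempting to go further and say that the error dilutes the response, pseudoprogression and immune-marker results, or exposes subjects to direct harm. The documents do not support either at a stated size. They give no count of affected subjects, which is probably small among 43, and they cite no safety mechanism for immunosuppressed subjects under this criterion. The protocol itself allows steroids up to the cap. The primary analysis is a descriptive estimate of sensitivity and specificity (Section 10.0), and none of its sample-size or precision figures changes.

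The conclusion assumes that the lead-in of Section 5.3 governs criterion 1 as it governs the rest of the list, and that the intended direction is the one the steroid exemption requires. The eligibility review form is not part of the documents, so whether it already corrects the wording is unknown.

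**What to change.** Reword criterion 1 to remove the negated clause, so that immunodeficiency and continuous immunosuppression are each addressed in the direction the sponsor intends and the steroid exemption follows logically. Simply joining the two conditions with an or, and keeping only the edema exemption, would create a new conflict: inclusion 5 also allows physiologic and prophylactic steroids, and criterion 6 exempts replacement therapy. The three passages must be reconciled together.

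Because Section 7.17 carries exclusion-list prohibitions into treatment, the amendment should also say how the reworded criterion sits with the corticosteroids and infliximab that Section 7.12 provides for immune-related events. Which rule is right is for the sponsor to decide.

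As a secondary change, state under criterion 15 that its discretion does not override criteria 6 and 19, or otherwise reconcile the three. Then align the eligibility review form.

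The cost is a wording amendment, its review-board approval and an updated form. A few subjects who could enter on the literal text might no longer qualify. No analysis or sample-size text needs to change.

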5.4 Subject Withdrawal/Discontinuation Criteria

Subjects who complete 2 years of treatment or 35 cycles (whichever comes later) will move into the Follow-Up Phase and should be assessed every 12 weeks (± 30 days) by clinical standard of care MRI scans and clinical assessment to monitor disease status for up to 1 year or until they progress or death. After 1 year, the imaging and clinical assessment time point will occur every 6 months (± 30 days) until death.

Subjects who a) attain a CR or b) complete 24 months of treatment with pembrolizumab may discontinue treatment with the option of restarting treatment if they meet the criteria specified in Section 7.11. After discontinuing treatment following assessment of CR, these subjects should return to the site for a Safety Follow-up Visit (described in Section 7.8) and then proceed to the Follow-Up Period of the study (described in Section 7.9).

Subject withdrawal includes patients who wish to withdraw consent for continuing on the study or who were lost to followup. Additionally, subjects may be discontinued from the trial for any of the following reasons:

- The subject or legal representative (such as a parent or legal guardian) withdraws consent.
- Confirmed progression in brain lesions or systemic disease (confirmed by imaging or tissue biopsy)
Note: A subject may be granted an exception to continue on treatment with confirmed radiographic progression if clinically stable or clinically improved, at the discretion of the treating physician. Please see Section 7.9
- Unacceptable adverse experiences as described in Section 9.0
- Miss two consecutive pembrolizumab treatments for any reason other than surgery.
- Intercurrent illness that prevents further administration of treatment including clinical deterioration at the discretion of the PI.
- Investigator's decision to withdraw the subject
- The subject has a confirmed positive serum or urine pregnancy test. If the urine test is positive, cannot be performed or cannot be confirmed negative, a serum pregnancy test will be required.
- Noncompliance with trial treatment or procedure requirements
- Administrative reasons

The end of treatment and follow-up visit procedures are listed in the schedule of events (Sections 6 and 7).

5.4.1 Early stopping rule

This is a pilot study evaluating an imaging biomarker. There is sufficient data regarding the safety and toxicities of ferumoxytol and pembrolizumab as well as the standard of care therapies; safety and toxicity data reading their combination is limited. The study team comprising of the PI and co-investigators, reviewed the toxicity data for arm 2 on March 29, 2019 prior to enrolling the 11th subject and there were no grade 3 or greater toxicities attributed to pembrolizumab, ferumoxytol, or both.

A second toxicity review will be performed prior to starting enrollment of the 18 additional subjects provided from the closing of the melanoma arm of the study, and after every 10 additional subjects are enrolled thereafter. The study will be terminated if more than 50% of the subjects enrolled at the time of the review have a grade 3 or greater toxicity that will be 1) definitely attributed to pembrolizumab, ferumoxytol, or both (attribution code of '3'); or 2) possibly attributed to pembrolizumab, ferumoxytol, or both (attribution code of '2'), unless they are definitely attributed (attribution code of '3') to standard of care therapy. To ensure compliance with the early stopping rule, all adverse events will be monitored and reported continuously by the study team in order to stop treatment as soon as a subject experiences grade 3 or greater AE attributed to pembrolizumab, ferumoxytol, or both.

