2.0 TRIAL DESIGN

This study will evaluate incidence, magnitude and timing of true vascular tumor progression, pseudoprogression and immune response to pembrolizumab in patients with primary brain tumors using ferumoxytol steady state MRI imaging.

Originally, the study had two arms:

ARM 1: Metastatic brain tumors - Metastatic melanoma

ARM 2: Primary brain tumors - Glioblastoma (GBM)

In December 2019, we decided to stop the enrollment to the melanoma arm and allocate the remaining 18 slots to the Glioblastoma arm – a total of 43 subjects will now be enrolled in the GBM arm.

Treatment

Subjects scheduled to receive standard of care stereotactic radiosurgery (SRS) for brain metastases in Arm 1 or standard of care chemoradiation (CRT) with temozolomide for GBM in Arm 2, are eligible. All subjects will receive pembrolizumab (200mg intravenous every 3 weeks) in addition to standard of care SRS or CRT in the respective arms, until toxicity, or persistent radiographic progression is confirmed, whichever comes first.

Imaging

All subjects will be scanned with clinical MRI at baseline prior to radiation, 4 weeks after the last day of radiation and every 9 weeks thereafter until completion or until taken off-study for

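### The toxicity stopping rule counts enrolled rather than exposed and observed subjects, schedules no look covering GBM subjects 36 to 43, and states no stopping probabilities

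*Combined protocol and SAP*

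**What the plan says.** Section 5.4.1 (Early stopping rule) sets a mandatory trial-level rule. The trial is "terminated if more than 50% of the subjects enrolled at the time of the review have a grade 3 or greater toxicity", provided the event is definitely attributed to pembrolizumab, ferumoxytol or both, or possibly attributed to them and not definitely due to standard of care.

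The review history and schedule are in the same section:

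- First review: the study team "reviewed the toxicity data for arm 2 on March 29, 2019". Ten subjects had been enrolled by then, and the finding was that "there were no grade 3 or greater toxicities attributed to pembrolizumab, ferumoxytol, or both".
- Second review, still ahead when this text was written: "A second toxicity review will be performed prior to starting enrollment of the 18 additional subjects" released by closing the melanoma arm.
- Further reviews follow "after every 10 additional subjects are enrolled thereafter".

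Section 2.0 fixes the size of the arm: "a total of 43 subjects will now be enrolled in the GBM arm".

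The rule sets no exposure or minimum follow-up requirement for the denominator. It does not say whether the 2 melanoma subjects, or unevaluable subjects replaced under section 5.4.3, are counted. Neither section 5.4.1 nor the SAP (section 10.0) gives the probability that the rule stops the trial at any true toxicity rate.

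**The concern.** Section 5.4.1 itself says that safety data on the combination are limited, and safety is the first secondary objective (section 3.2). This is the only trial-level safety criterion with a number in it, so readers will take it as the safeguard.

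Three features weaken it:

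- **Timing.** Reviews are triggered by enrolment, while pembrolizumab starts around the first day of radiation (section 6.0). The newest subjects enter the denominator before they can have had a pembrolizumab event, and recently treated subjects enter after little observation.
- **Carry-over.** The count is cumulative, so later toxicity is averaged with 10 subjects who had no attributed grade 3 or greater event at the first review.
- **Coverage.** The last review that falls within the planned sample leaves 8 subjects outside any scheduled application of the rule.

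At stake is whether a rate above the protocol's own limit in later subjects would trigger the termination that the protocol promises, and whether the DSMC can judge this from the document.

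**Working it through.** The plan prints no figure for this rule, so there is none to reproduce.

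**Review sizes.** Second review: 43 − 18 = 25 enrolled (derived, not stated). Next: 25 + 10 = 35. Next: 45, which exceeds 43. Subjects without a scheduled look: 43 − 35 = 8.

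**Events needed.** More than 50% of 25 is more than 12.5, so at least 13. More than 50% of 35 is more than 17.5, so at least 18. If the first 10 contribute no events:

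- at 25 enrolled: 13 of the next 15, or 87%;
- at 35 enrolled: 18 of the next 25, or 72%.

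**Stopping probability.** Assume that subjects 11 onward have independent events with probability p. The documents give no expected rate, so p is an assumption shown over a range. With X ~ Bin(15, p) for subjects 11–25 and Y ~ Bin(10, p) for subjects 26–35:

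P(stop by 35) = P(X ≥ 13) + Σ over k ≤ 12 of P(X = k) × P(Y ≥ 18 − k).

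If the first 10 carry the same eventual risk, replace X by Bin(25, p), still with limits 13 and 18. For u unexposed subjects at each review, remove u from those at risk and leave the denominator unchanged. With u = 2 and the first 10 event-free, the first of these reviews needs 13 of 13, which at p = 0.6 has probability 0.6^13 = 0.13%.

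Cumulative chance of stopping by 35:

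| True rate p | First 10 event-free, all exposed | First 10 event-free, 2 unexposed at each review | First 10 same risk, all exposed | First 10 same risk, 2 unexposed at each review |
|---|---|---|---|---|
| 40% | 0.1% | <0.1% | 18.3% | 10.4% |
| 50% | 2.3% | 0.5% | 58.7% | 43.6% |
| 60% | 15.7% | 5.4% | 91.5% | 83.1% |
| 70% | 51.7% | 26.9% | 99.6% | 98.5% |
| 80% | 89.2% | 69.5% | >99.9% | >99.9% |

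**How many might be unexposed.** Section 1.0 plans 45 subjects in 3 years: 45/36 = 1.25 a month. Screening is within 28 days of first treatment, which gives 1.25 × 28/30.4 ≈ 1.2 subjects waiting. Adding the 15-day window gives 1.25 × 43/30.4 ≈ 1.8. One or two is therefore plausible at the planned pace. This counts only the wait for a first dose, not short follow-up after it.

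**Melanoma subjects.** If the 2 melanoma subjects were counted and event-free, the limits become 14/27 and 19/37. With the first 10 event-free and all exposed, the chance of stopping by 35 falls to 7.4% at 60% and 34.2% at 70%.

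**Adding a look at 43.** More than 21.5 means at least 22 events. With all subjects exposed, the cumulative chance becomes 4.7% at 50%, 29.4% at 60%, 74.6% at 70% and 98.0% at 80% if the first 10 stay event-free. It becomes 63.3% at 50% and 94.3% at 60% if they share the risk.

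**The case against.** **The low figures depend on the first 10 staying event-free.** The March 2019 finding was a snapshot, and section 7.4 allows up to 2 years of treatment, so those subjects could still add events. A jump from 0 of 10 to 50–60% on the same regimen also needs an explanation that the documents do not offer. Zero of 10 has an exact 95% interval of 0% to 31%, and its probability at a constant 50% rate is 0.5^10 = 0.1%. This stands: the two assumptions about the first 10 are bracketing cases, and both belong in the conclusion.

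**A reader might infer that the rule would rarely stop the trial even at very high toxicity.** The figures do not support that. In the less favourable case, with prompt exposure, it stops about half the time at 70% and 89% of the time at 80%. Nor is the low stopping chance at 40% a failure, since 40% lies below the protocol's own limit.

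**A reader might infer that the last 8 subjects go unmonitored.** They do not. Sections 5.4.1 and 9.1 provide continuous monitoring to stop treatment in an affected subject. Section 5.4.4 allows early termination when the incidence or severity of adverse reactions suggests a health hazard. Under section 12.5 the DSMC reviews toxicity every 6 months and may suspend the study. Replacement of unevaluable subjects might also bring a review at 45. What remains is that none of these routes has a numeric boundary, and the replacement route depends on a counting convention that the protocol does not state.

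**This is a descriptive pilot.** That is true, but the sponsor chose a mandatory termination rule, and its denominator and coverage should let it work as intended.

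**Conclusion.** The point holds as a defect in a stated rule. Two parts need no assumption about toxicity: the denominator treats unexposed and barely observed subjects as event-free, and no scheduled look covers subjects 36 to 43 if enrolment ends at 43. The absence of stopping probabilities is likewise plain from the text.

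The size is conditional. With independent events, reviews at 25 and 35 and all subjects exposed, a 60% rate in subjects 11 onward stops the trial about 16% of the time if the first 10 stay event-free and about 91% if they share the risk. Two unexposed subjects at each review reduce the first figure to about 5%. The documents do not settle which assumption about the first 10 is nearer the truth, so neither figure should be quoted alone.

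**What to change.** Amend section 5.4.1 as follows.

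1. Make the denominator subjects who have received pembrolizumab or ferumoxytol and completed a stated minimum observation period. Count a subject with an earlier qualifying event from that event, so that the observation requirement cannot drop events. State whether melanoma and replaced subjects are included.
2. Add a scheduled review covering subjects 36 to 43. Enrolment would be complete by then, but treatment can run for up to 2 years, so the review can still lead to action.
3. Print a small table of stopping probabilities across a range of true rates, under both assumptions about the first 10.
4. At each review, show the rate in subjects since the previous review descriptively to the study team and DSMC. It should not be a second automatic trigger. Applying the 50% limit separately to subjects 11–25 (8 of 15) and 26–35 (6 of 10) would stop 1 − (1 − 0.213)(1 − 0.166) = 34% of trials at a 40% rate, against 0.1% to 18% now.

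The toxicity limit itself remains for the clinical team and DSMC to set. The cost is a wording change, one small table and one extra review. The observation period also means that each review counts somewhat fewer subjects than are enrolled on that date.
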